## **7.0 Statistical Considerations**

### **7.1 Study design**

This study is a global, multi-center, post-market observational study to demonstrate the safety and performance of the Wright products listed in Section 3.3. Data will be collected at baseline, surgery, at the last scheduled standard of care and/or surgeon release follow-up (FU) time point. The subjects improvement in post-surgical quality of life will be assessed using EQ-5D-5L and Foot and Ankle Ability Measure (FAAM).

An adverse event resulting from the presence or performance of the device and removal due to implant failure will determine the survivorship of the Wright product. Further, safety will be assessed by subject experience of device complication and adverse events during the study period.

All effectiveness and safety analysis will be performed separately for each Wright Medical device included in the study.

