### **7.3 Data Analysis**

Improvements in subject quality of life after surgery will be assessed by constructing 95% confidence interval for the mean change from baseline score in EQ-5D-5L and FAMM total and component scores.

|   |  |  |
|---|--|--|
|  | Clinical Investigation Plan
Foot and Ankle Products | CIP- INT19-MDR-001
Version: 2 |
|---|--|--|

Survivorship of a Wright product will be assessed based on adverse event resulting from the presence or performance of the device. The Kaplan Meier survivorship method and life table analysis will be employed. Time to adverse event due to the presence or performance of the implant will be the survivorship endpoint for each Wright device. Also, time to reoperation to exchange or remove any part of the Wright device due to failure of the implant will also determine the Wright product survivorship. Subjects who will not experience these events will be censored at the last follow-up visit. The Kaplan Meier survival curve and the 95% Confidence Interval will be constructed.

Safety endpoints will include all adverse events (AE), serious AE (SAE), unanticipated adverse device effects (UADEs).

All subjects enrolled in the study will be assessed for safety. Adverse events and other safety evaluations will be reported as frequency and rates as appropriate, cumulative over the different follow-up schedules.

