### 3. Statistical Procedure

#### 3.1. FRAMEWORK

The purpose of this statistical analysis plan is to guide the analysis and production of statistical output for the Wright Foot & Ankle Post-Market Observational Study. The company decided to discontinue enrollment to the study on November 1, 2021. At study end date, there were 122 patients enrolled in the study. The sample size of 40 patients per device that was originally planned in the study was therefore not met.

The study required at least 40 sample size for each Wright medical device (See INT19-MDR-001 Protocol, Version 3). For the same sample size parameters in the protocol  $n=10$ , will yield a power of 0.5. Thus, for the purpose of reporting statistically valid outcomes, descriptive summary statistics will be presented for Wright devices implanted in at least 10 patients enrolled in the study. Patient data on devices that has less than 10 implanted patients will be provided in the listings to be made available for future study or reference. Appendix Table 1 lists the Wright devices that are included in the study.

As the goal of the study is to determine the performance and safety of each device under investigation, analysis of outcomes will be done for each device the patient received. Note that a patient may have received more than one of the Wright devices. In all analysis of outcomes, patient level data will be included in the analysis for each device he/she received.

All analysis to be conducted are of descriptive nature only. No test of hypothesis will be performed. All quantitative variables, including those based on calculations (i.e., improvement from baseline), will be analyzed with a case summary evaluation before the detailed characteristics and parameter can be evaluated. A case summary contains a listing of the number of valid cases/values, missing cases/values (if any) and total cases/values in the specific analysis. The mean and median will be reported to assess the average or centrality of quantitative variables. Improvement from baseline in patient reported outcome (PROM) will be assessed at each post-surgery visit. Improvement will be based on the difference in raw scores.

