Whenever the available data allows, the standard deviation, interquartile range (IQR) and maximum and minimum will be calculated. All quantitative variables will be assessed for normality via the Shapiro-Wilk test. The 95% confidence interval (CI) of the mean will be presented when the normality of the data is met.

All qualitative variables, including those based on summaries (secondary elements), will be analyzed listing the proportions, frequencies, column and row totals and missing proportion (if any).

The proportion of device surviving at each visit will be summarized for each device. Rates will be computed based on available data. Missing data will not be imputed.

No imputations for missing data will be conducted.

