### 6.6. HARMS AND SAFETY

See [Table 5.1](#). The safety of each device will be summarized in the interim and final report. Overall summary of adverse events will be presented for each device. Total frequencies and percentages of adverse events for each Wright device will be summarized for the following factors:

- Procedure-Related Adverse Event / Incident
- Device-Related Adverse Event / Incident
- Device Failure
- Unanticipated Adverse Device Event
- Serious Adverse Event (SAE)
- Hospitalization SAE Outcome
- Treatment Required for the AE

The occurrence and rate of SAE will be further categorized by the outcome of the SAE (i.e., death, hospitalization).

The rates for device failure will be the basis of the survival rates for each device. The above AE factors will also be summarized for each study site.

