## 8.2. Appendix 2 – Listing of Tables and Listings, Table Templates

### A. LISTING OF TABLES

Table	1.1	Subject Accounting
Table	1.2	Subject Eligibility
Table	1.3	Demographics and Clinical Characteristics
Table	1.4	All Protocol Deviations
Table	1.5	Medical History
Table	2.1	Surgical and Operative Information
Table	2.2	Additional Surgical Procedures Performed
Table	3.1	EQ-5D by device and visit
Table	3.2.1	FAAM score by device and visit
Table	3.2.2	FAAM overall rating by Device and Visit
Table	4.1	Surgeon assessment by device
Table	4.2	Radiographic assessment by device
Table	5.1	Life table for time to first device related adverse event by device
Table	5.2	Life table for device failure by device
Table	5.3	Life table for time to death by device
Table	6.1	Adverse event by device

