**Table 5.1 Adverse Events by device.**

Adverse Events	Device 1		...		Device k	
	Subjects (%)	Events	Subjects (%)	Events	Subjects (%)	Events
Procedure-Related	xx (xx.x%)	xx			xx (xx.x%)	xx
Device-Related	xx (xx.x%)	xx			xx (xx.x%)	xx
Device Failure	xx (xx.x%)	xx			xx (xx.x%)	xx
Unanticipated AE	xx (xx.x%)	xx			xx (xx.x%)	xx
Serious AE	xx (xx.x%)	xx			xx (xx.x%)	xx
Hospitalization	xx (xx.x%)	xx			xx (xx.x%)	xx
Death	xx (xx.x%)	xx			xx (xx.x%)	xx
Required Treatment	xx (xx.x%)	xx			xx (xx.x%)	xx
Physical Therapy	xx (xx.x%)	xx			xx (xx.x%)	xx
Medication	xx (xx.x%)	xx			xx (xx.x%)	xx
Surgery	xx (xx.x%)	xx			xx (xx.x%)	xx
Other	xx (xx.x%)	xx			xx (xx.x%)	xx

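### Read literally, SAP 3.1 counts one device's failure, device-related event or UADE against every co-implanted study device

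*SAP*

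**What the plan says.** SAP 3.1 states "Note that a patient may have received more than one of the Wright devices" and follows this with the rule "In all analysis of outcomes, patient level data will be included in the analysis for each device he/she received". The same section adds "The proportion of device surviving at each visit will be summarized for each device".

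SAP 6.6 summarizes events for each device. The factors include device-related events, device failure and UADEs, alongside procedure-related events and serious adverse events. It then says "The rates for device failure will be the basis of the survival rates for each device". The template "Table 5.1 Adverse Events by device" gives subjects and events in one column pair per device. The table list in Appendix 2A adds by-device life tables for first device-related adverse event, for device failure ("Life table for device failure by device") and for death.

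The protocol sets the target. Section 7.1: "All effectiveness and safety analysis will be performed separately for each Wright Medical device included in the study". Section 7.3: "Time to adverse event due to the presence or performance of the implant will be the survivorship endpoint for each Wright device". Section 7.3 also counts a reoperation that exchanges or removes part of a device because that implant failed.

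On attribution, protocol 11.2 has relatedness to the device or the procedure reported on the adverse event form. Protocol 11.3 lists a device-related item and a narrative among the items collected. Under protocol 11.4.2 the sponsor determines in writing how each event relates to the implanted components. If sponsor and investigator disagree, both opinions are communicated, or independent review is sought as needed.

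**The concern.** The SAP rule covers every analysis of outcomes and carries no exception. Device failure and device-related events are outcomes, so a programmer who follows the sentence would enter one device's failure under each study device that the patient has. The protocol's endpoint asks something narrower: whether this implant caused an event or failed.

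The SAP gives its goal as the performance and safety of each device, and failure rates feed each device's survival rate. The analyses are descriptive, so the harm would be a misleading safety column rather than a wrong test. SAP 3.1 summarizes devices implanted in as few as 10 patients, where a single misplaced event shows clearly.

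**Working it through.** The plan states no figure for this point, so there is none to reproduce. The check compares the texts and then illustrates the size.

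**1. Which outcomes are affected**

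| Outcome by device | Effect of entering it under every device received |
|---|---|
| Denominators, EQ-5D, FAAM | None: these describe recipients of the device |
| All-cause adverse events, serious adverse events, death | None: these are patient-level events among recipients |
| Procedure-related events | None: these are tied to the operation |
| Device-related events, device failure, UADEs, and the life tables for first device-related event and device failure | Affected: the event belongs to a particular device |

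**2. One patient followed through.** Suppose a patient has study devices A and B, and A fails and is removed while B stays in place. Protocol 6.2.2 foresees this situation, because it keeps a subject in the study when other study devices remain.
- Protocol 7.3 endpoint: A has one failure and B has none. B is censored at the last follow-up visit.
- SAP 3.1 read literally: A has one failure and B has one failure, although B has not failed.

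**3. Size of one carried-over event.** Inputs: n = 10 is the reporting threshold in SAP 3.1. n = 20 and the single carried-over event are assumptions. The device is taken to have no event of its own. Exact two-sided 95% limits: for x = 0, the upper limit is 1 − 0.025^(1/n). For x = 1, the lower limit is 1 − 0.975^(1/n) and the upper limit is the 0.975 quantile of Beta(2, n − 1).

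| n | Own events | With one carried over | Crude survival |
|---|---|---|---|
| 10 | 0/10 (0 to 30.8%) | 1/10 = 10% (0.3 to 44.5%) | 100% to 9/10 = 90% |
| 20 | 0/20 (0 to 16.8%) | 1/20 = 5% (0.1 to 24.9%) | 100% to 19/20 = 95% |

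The SAP does not plan these intervals. They show only how little a column of this size can absorb.

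**4. Range over assumed overlap.** Assume that every recipient has m study devices, each with independent event risk p. The rate charged to each device is then 1 − (1 − p)^m.

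| p | m = 1 | m = 2 | m = 3 |
|---|---|---|---|
| 2% | 2.0% | 1 − 0.98² = 3.96% | 1 − 0.98³ = 5.88% |
| 5% | 5.0% | 1 − 0.95² = 9.75% | 1 − 0.95³ = 14.26% |

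With one device per patient there is no distortion. Counting only against the responsible device returns p in every cell. The documents give neither p nor m.

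**The case against.** The best defence is that the sentence is an inclusion rule. It speaks of patient-level data, and it comes soon after a statement that outcomes are analysed for each device received. A device-failure row under a device heading would ordinarily mean failure of that device. The protocol points the same way: 7.3 ties the endpoint to the implant, 11.1.3 judges a UADE against the applicable product information, 11.4.2 relates events to components, and 6.3.5.2 records a product code and lot number for each component. The output is descriptive, any error would overstate risk, and Listing 9 shows the individual events.

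Much of this stands. It makes attribution the likely intention and limits the consequence. It does not settle the count, because the inclusion-only reading is unwritten and the only written rule, taken at its word, gives the other result.

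Three stronger readings are tempting but not supported:
- A reader might infer that events will be miscounted. The documents show an unrestricted rule, not a miscount.
- A reader might infer that the adverse event form cannot identify the device. Protocol 11.3 lists what the collected information will include and names no device identifier there, but the form itself is not shown.
- A reader might infer that the whole SAP lacks an attribution rule. Some of its pages were not available, so the absence can be stated only for the text at hand.

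**Conclusion.** The point holds as a rule that is too broad as written. On a literal reading, SAP 3.1 carries device-specific events across to co-implanted devices. This conflicts with the per-device survivorship endpoint in protocol 7.3, and the available SAP text nowhere restricts it. The direction is clear: event rates too high and survival too low for a device that did not cause the event.

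The size is unknown and is zero without co-implantation. The move from 0/10 to 1/10 rests on one assumed carried-over event at the SAP's own reporting threshold. The multi-device rates rest on assumed values of p and m and on independence. The point is worth correcting because the by-device columns are the study's result and the correction is cheap. Confidence is medium, since the inclusion-only meaning may have been intended.

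**What to change.** Change the wording in SAP 3.1 and 6.6:
- Limit the patient-level rule to denominators, patient-reported outcomes, and all-cause and procedure-related adverse events.
- Count device-related adverse events, device failures, UADEs and the matching life-table events only under the device or devices judged responsible.
- Base that judgement on existing records: the investigator's form and narrative (protocol 11.2 and 11.3) and the sponsor's documented determination (protocol 11.4.2).
- If the responsible device cannot be determined, or the investigator and sponsor still disagree after the protocol 11.4.2 process (including independent review where sought), count the event under each possibly responsible study device with a footnote. A later judgement by the sponsor then cannot remove events from the columns.
- Report the number of multi-device patients for each device.

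The cost is two SAP wording changes and a small check of adverse event records among 122 patients to see whether each names the component. Some footnoted events will still appear under more than one device.

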### 3.1.1. Primary Analysis / Endpoint

Improvements in subject quality of life after surgery will be assessed by constructing 95% confidence interval for the mean change from baseline score in EQ-5D-5L.

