### 3.1.2. Secondary Analyses

FAAM score improvements from baseline will be summarized with 95% confidence interval for the mean.

Safety of Wright medical products will be assessed by the frequency and rates of the with collected AE safety profiles.

Surgeon and patient assessment of Wright devices will be presented descriptively.

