**Table 2.1. Surgical and Operative Information**

Factors	Device 1	Device 2	...	Device k
	Freq (%)	Freq (%)		Freq (%)
Indication for use				
Post traumatic	xx(xx.x%)	xx(xx.x%)		xx(xx.x%)
Arthritis	xx(xx.x%)	xx(xx.x%)		xx(xx.x%)
Fracture	xx(xx.x%)	xx(xx.x%)		xx(xx.x%)
Fusion	xx(xx.x%)	xx(xx.x%)		xx(xx.x%)
Reconstruction/Correction	xx(xx.x%)	xx(xx.x%)		xx(xx.x%)
Revision procedure	xx(xx.x%)	xx(xx.x%)		xx(xx.x%)
Instability	xx(xx.x%)	xx(xx.x%)		xx(xx.x%)
Skeletal defect after tumor selection	xx(xx.x%)	xx(xx.x%)		xx(xx.x%)
Prior surgery				
Yes	xx(xx.x%)	xx(xx.x%)		xx(xx.x%)
No	xx(xx.x%)	xx(xx.x%)		xx(xx.x%)
Location of Surgery				
Right	xx(xx.x%)	xx(xx.x%)		xx(xx.x%)
Left	xx(xx.x%)	xx(xx.x%)		xx(xx.x%)

Table 3.1 EQ-5D by device and visit

Wright Device	Visit		
	Baseline (n=xx)	Post-op Visit 1 (n=xx)	Post-op Visit 2 (n=xx)
Device 1			
Overall Health			
mean±sd	xx.x±xx.x	xx.x±xx.x	xx.x±xx.x
median	xx.x	xx.x	xx.x
min,max	xx.x, xx.x	xx.x, xx.x	xx.x, xx.x
95% CI	(xx.x, xx.x)	(xx.x, xx.x)	(xx.x, xx.x)
Index Value	xx.x	xx.x	xx.x
mean±sd	xx.x±xx.x	xx.x±xx.x	xx.x±xx.x
median	xx.x	xx.x	xx.x
min,max	xx.x, xx.x	xx.x, xx.x	xx.x, xx.x
95% CI	(xx.x, xx.x)	(xx.x, xx.x)	(xx.x, xx.x)
Change from Baseline			
Overall Health			
mean±sd		xx.x±xx.x	xx.x±xx.x
median		xx.x	xx.x
min,max		xx.x, xx.x	xx.x, xx.x
95% CI		(xx.x, xx.x)	(xx.x, xx.x)
Index Value		xx.x	xx.x
mean±sd		xx.x±xx.x	xx.x±xx.x
median		xx.x	xx.x
min,max		xx.x, xx.x	xx.x, xx.x
95% CI		(xx.x, xx.x)	(xx.x, xx.x)
Device 2			
Overall Health			
mean±sd	xx.x±xx.x	xx.x±xx.x	xx.x±xx.x
median	xx.x	xx.x	xx.x
min,max	xx.x, xx.x	xx.x, xx.x	xx.x, xx.x
95% CI	(xx.x, xx.x)	(xx.x, xx.x)	(xx.x, xx.x)
Index Value	xx.x	xx.x	xx.x
mean±sd	xx.x±xx.x	xx.x±xx.x	xx.x±xx.x
median	xx.x	xx.x	xx.x
min,max	xx.x, xx.x	xx.x, xx.x	xx.x, xx.x
95% CI	(xx.x, xx.x)	(xx.x, xx.x)	(xx.x, xx.x)
Change from Baseline			
Overall Health			
mean±sd		xx.x±xx.x	xx.x±xx.x
median		xx.x	xx.x
min,max		xx.x, xx.x	xx.x, xx.x
95% CI		(xx.x, xx.x)	(xx.x, xx.x)
Index Value		xx.x	xx.x
mean±sd		xx.x±xx.x	xx.x±xx.x
median		xx.x	xx.x
min,max		xx.x, xx.x	xx.x, xx.x
95% CI		(xx.x, xx.x)	(xx.x, xx.x)
:			

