**Table 3.2.1 FAAM score by device and visit.**

Wright device	Baseline				Follow-up Visit				Final Visit			
	n	mean±sd	min,max	95% CI	n	mean±sd	min,max	95% CI	n	mean±sd	min,max	95% CI
Device 1												
FAAM SANE	xx	xx.x±xx.x	xx.x, xx.x	(xx.x, xx.x)	xx	xx.x±xx.x	xx.x, xx.x	(xx.x, xx.x)	xx	xx.x±xx.x	xx.x, xx.x	(xx.x, xx.x)
Sports Subscale	xx	xx.x±xx.x	xx.x, xx.x	(xx.x, xx.x)	xx	xx.x±xx.x	xx.x, xx.x	(xx.x, xx.x)	xx	xx.x±xx.x	xx.x, xx.x	(xx.x, xx.x)
ADL Subscale	xx	xx.x±xx.x	xx.x, xx.x	(xx.x, xx.x)	xx	xx.x±xx.x	xx.x, xx.x	(xx.x, xx.x)	xx	xx.x±xx.x	xx.x, xx.x	(xx.x, xx.x)
Change from Baseline												
FAAM SANE					xx	xx.x±xx.x	xx.x, xx.x	(xx.x, xx.x)	xx	xx.x±xx.x	xx.x, xx.x	(xx.x, xx.x)
Sports Subscale					xx	xx.x±xx.x	xx.x, xx.x	(xx.x, xx.x)	xx	xx.x±xx.x	xx.x, xx.x	(xx.x, xx.x)
ADL Subscale					xx	xx.x±xx.x	xx.x, xx.x	(xx.x, xx.x)	xx	xx.x±xx.x	xx.x, xx.x	(xx.x, xx.x)
Device 2												
FAAM SANE	xx	xx.x±xx.x	xx.x, xx.x	(xx.x, xx.x)	xx	xx.x±xx.x	xx.x, xx.x	(xx.x, xx.x)	xx	xx.x±xx.x	xx.x, xx.x	(xx.x, xx.x)
Sports Subscale	xx	xx.x±xx.x	xx.x, xx.x	(xx.x, xx.x)	xx	xx.x±xx.x	xx.x, xx.x	(xx.x, xx.x)	xx	xx.x±xx.x	xx.x, xx.x	(xx.x, xx.x)
ADL Subscale	xx	xx.x±xx.x	xx.x, xx.x	(xx.x, xx.x)	xx	xx.x±xx.x	xx.x, xx.x	(xx.x, xx.x)	xx	xx.x±xx.x	xx.x, xx.x	(xx.x, xx.x)
Change from Baseline												
FAAM SANE					xx	xx.x±xx.x	xx.x, xx.x	(xx.x, xx.x)	xx	xx.x±xx.x	xx.x, xx.x	(xx.x, xx.x)
Sports Subscale					xx	xx.x±xx.x	xx.x, xx.x	(xx.x, xx.x)	xx	xx.x±xx.x	xx.x, xx.x	(xx.x, xx.x)
ADL Subscale					xx	xx.x±xx.x	xx.x, xx.x	(xx.x, xx.x)	xx	xx.x±xx.x	xx.x, xx.x	(xx.x, xx.x)
:												
Device k												
FAAM SANE	xx	xx.x±xx.x	xx.x, xx.x	(xx.x, xx.x)	xx	xx.x±xx.x	xx.x, xx.x	(xx.x, xx.x)	xx	xx.x±xx.x	xx.x, xx.x	(xx.x, xx.x)
Sports Subscale	xx	xx.x±xx.x	xx.x, xx.x	(xx.x, xx.x)	xx	xx.x±xx.x	xx.x, xx.x	(xx.x, xx.x)	xx	xx.x±xx.x	xx.x, xx.x	(xx.x, xx.x)
ADL Subscale	xx	xx.x±xx.x	xx.x, xx.x	(xx.x, xx.x)	xx	xx.x±xx.x	xx.x, xx.x	(xx.x, xx.x)	xx	xx.x±xx.x	xx.x, xx.x	(xx.x, xx.x)
Change from Baseline												
FAAM SANE					xx	xx.x±xx.x	xx.x, xx.x	(xx.x, xx.x)	xx	xx.x±xx.x	xx.x, xx.x	(xx.x, xx.x)
Sports Subscale					xx	xx.x±xx.x	xx.x, xx.x	(xx.x, xx.x)	xx	xx.x±xx.x	xx.x, xx.x	(xx.x, xx.x)
ADL Subscale					xx	xx.x±xx.x	xx.x, xx.x	(xx.x, xx.x)	xx	xx.x±xx.x	xx.x, xx.x	(xx.x, xx.x)

Note:

ADL - activities of daily living

SANE - single assessment numeric evaluation

Tale 3.2.2 FAAM overall rating by device and visit

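### SAP 3.1 shows the 95% CI of the mean only if a normality test is passed, while SAP 3.1.1, 3.1.2, protocol 7.3 and the table shells require that CI without condition

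*SAP*

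**What the plan says.** SAP 3.1 sets the general rule. It defines its scope broadly: "All quantitative variables, including those based on calculations (i.e., improvement from baseline), will be analyzed with a case summary evaluation". All quantitative variables are to be checked with Shapiro-Wilk, after which "The 95% confidence interval (CI) of the mean will be presented when the normality of the data is met". The same section states "No test of hypothesis will be performed".

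The endpoint-specific text carries no such condition:

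- SAP 3.1.1 (primary): improvement in quality of life "will be assessed by constructing 95% confidence interval for the mean change from baseline score in EQ-5D-5L".
- SAP 3.1.2 (secondary): "FAAM score improvements from baseline will be summarized with 95% confidence interval for the mean".
- Protocol 7.3: improvement is "assessed by constructing 95% confidence interval for the mean change from baseline score in EQ-5D-5L" and in the FAAM total and component scores.
- SAP Appendix 2: the shells headed "Table 3.1 EQ-5D by device and visit" and "Table 3.2.1 FAAM score by device and visit" have fixed 95% CI cells for change from baseline, with no normality footnote. Tables 1.3 and 4.2 also have fixed CI columns.

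**The concern.** Improvement from baseline is named as a quantitative variable, so the condition in SAP 3.1 reaches the primary and secondary change scores. Where Shapiro-Wilk does not reject, both instructions can be followed. Where it rejects, SAP 3.1 leaves the CI out and the other places require it. Nothing says which prevails, at what level the test is judged, or what interval takes the CI's place.

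The CI for mean EQ-5D change is the primary analysis as SAP 3.1.1 defines it. Under SAP 3.1 its appearance for a given device and visit would depend on the data, and two programmers could produce different tables from the same dataset. The condition may look like a safeguard for the t interval, so the check below also asks whether it improves the coverage of the intervals that are displayed.

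**Working it through.** **1. The texts side by side**

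| Place | Applies to | Condition on the 95% CI |
|---|---|---|
| SAP 3.1 | all quantitative variables, including improvement from baseline | normality by Shapiro-Wilk; no level and no substitute interval |
| SAP 3.1.1 | mean change in EQ-5D-5L | none |
| SAP 3.1.2 | mean FAAM improvement | none |
| Protocol 7.3 | mean change in EQ-5D-5L and FAAM | none |
| SAP Tables 3.1, 3.2.1 | EQ-5D and FAAM, by visit and change | none |
| SAP Tables 1.3, 4.2 | age and body size; radiographic angles | none |

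**2. The plan's own figure**

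Protocol 7.2 sizes each device group on the precision of a CI for mean EQ-5D (alpha 0.05 two-sided, half width 0.1, SD 0.313):

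n = (1.960 × 0.313 / 0.1)² = 37.63, rounded up to 38. This reproduces the protocol.

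So the study was planned around the kind of interval that SAP 3.1 can withhold. At n = 10, the SAP's floor for reporting a device, the t-based half width at the same SD is 2.262 × 0.313 / √10 = 0.224, more than twice the planned 0.1.

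**3. How often the CI would be withheld**

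The documents give neither a test level nor a distribution for change scores, so both are assumed. Each cell has 40,000 simulated datasets. The change score has mean 0.15 and SD 0.313 (the protocol's post-operative SD, assumed here for change). The shapes are normal, gamma with shape 4 (skewness 1) and gamma with shape 2 (skewness 1.41). An EQ-5D-like version draws baseline N(0.55, 0.313) and follow-up N(0.70, 0.313) with correlation 0.4, caps each at 1 and takes the difference. The interval is mean ± t(0.975, n−1) × SD/√n, withheld when Shapiro-Wilk p < 0.05.

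| Change score | n = 10 | n = 15 | n = 20 | n = 40 |
|---|---|---|---|---|
| Normal | 4.8% | 4.8% | 5.1% | 5.1% |
| EQ-5D-like, capped | 5.2% | 5.1% | 5.2% | 5.2% |
| Skewness 1 | 13.7% | 21.4% | 29.2% | 58.0% |
| Skewness 1.41 | 23.9% | 38.6% | 53.1% | 88.2% |

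A second EQ-5D-like version with means 0.40 and 0.75 gave 4.9–5.3%. The n = 40 column is the planned size, which the SAP says was not met.

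**4. Coverage of the 95% t interval, n = 10 to 40**

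| Change score | Always shown | Among those shown under SAP 3.1 |
|---|---|---|
| Normal, EQ-5D-like | about 95% | about 95% |
| Skewness 1 | 93.5–94.5% | 92.6–93.4% |
| Skewness 1.41 | 92.5–94.2% | 90.2–91.5% |

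The smallest displayed set has 4,710 datasets (skewness 1.41, n = 40, coverage 90.2%), with Monte Carlo SE √(0.902 × 0.098 / 4,710) = 0.43 points. A separate run of 20,000 datasets gave 88.7% for that cell on about 0.119 × 20,000 = 2,380 displayed intervals (SE 0.65 points); the direction is the same.

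That run also tried two more extreme shapes:

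- Exponential (skewness 2): withheld 44% at n = 10 and 84% at n = 20. Coverage falls from 90.0% to 87.2% and from 92.1% to 85.9%.
- 35% exact zeros mixed with N(0.3, 0.3): withheld 44%, 68% and 92% at n = 10, 20 and 40. Coverage is 93.3%, 94.3% and 95.0% if always shown, against 94.7%, 94.5% and 93.8% among those shown.

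For the gamma and exponential shapes the condition lowers coverage. A sample from a long-tailed distribution passes the test mainly when it happens to miss the tail, and such samples misplace the mean and understate the SD. The zero-heavy mixture is the exception, with a gain at n = 10, little difference at n = 20 and a loss at n = 40.

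**The case against.** The strongest reply is that the texts can be harmonised. SAP 3.1.1 and 3.1.2 are subsections of 3.1, so a framework display rule may govern them without being repeated; or the specific primary-analysis sentence may override a general rule written for variables such as age and weight. The sentence also does not say that the CI appears only in that case. Each reading is possible, but the SAP chooses neither. Under the first, a non-normal change score has no primary result in the form SAP 3.1.1 defines, and the SAP departs from protocol 7.3. Under the second, the condition does not apply to the endpoints that matter. If the CI is shown regardless, the sentence has no function.

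Other points carry some weight:

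- Shells guide programming and rarely carry conditions, so they are weaker evidence than SAP 3.1.1 and 3.1.2.
- The Table 3.1 shell keeps the median, minimum and maximum, so a non-normal EQ-5D change is still summarised. The Table 3.2.1 shell has no median.
- Shapiro-Wilk can be seen as a diagnostic and not as one of the hypothesis tests the SAP rules out. Here, though, its result decides what is reported.
- The large withholding rates need skewed or zero-heavy change scores, which the documents neither show nor exclude.
- An unconditional t interval is not exact under strong skew in small groups: 90.0% coverage for exponential data at n = 10.
- SAP 3.1 cites protocol Version 3, but the SAP front page names Version 2, which is the version available. The comparison with protocol 7.3 is therefore with Version 2.

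These limit the size of the problem. They do not supply the missing rule.

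**Conclusion.** The point holds: SAP 3.1 is wrong as written and should be fixed. The contradiction in the text is certain and rests on no assumption. Its practical size is not certain. It is about 5% of CIs if change scores are near-symmetric, and 14–29% (skewness 1) or 24–53% (skewness 1.41) for groups of 10 to 20 patients, all at an assumed test level of 0.05. Under those two skewed shapes the displayed intervals cover less well than the full set would, by roughly one to three points, so the condition gives no protection there.

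The consequence is moderate. The analysis is descriptive, no decision rule depends on the CI, and n, mean and SD would still let a reader rebuild it. No sample size changes.

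**What to change.** In SAP 3.1, delete the normality condition from the sentence on the 95% CI of the mean. State instead that the t-based 95% CI for mean change in the EQ-5D index, the EQ-5D overall health score and the FAAM scores of Table 3.2.1 is reported for every device and visit that is summarised. The same deletion brings SAP 3.1 into line with the CI columns of Tables 1.3 and 4.2.

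If Shapiro-Wilk is kept, describe it as a note that does not decide what is displayed. A bootstrap interval or an interval for the median may be added as a supplement where skew is marked, but should not replace the primary CI.

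Cost: one SAP sentence. The shells already contain the CI cells. No protocol amendment and no further patients are needed.

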## SURGEON ASSESSMENT AND RADIOGRAPHIC OUTCOME

See [Table 4.1](#). At the final visit of the patient, the attending surgeon assessed the surgical foot to assess the outcome. The surgeon also assessed the radiographic outcome of the surgery. For each Wright device of interest, the following will be summarized:

- Days from surgery to radiographic evaluation
- Imaging procedure done: standing AP/lateral, hindfoot alignment view, CT, MRI, Other
- Surgeon opinion on Wright product performance
- Bony union outcome for joint arthrodesis device

See [Table 4.2](#). The surgeon assessment of angle deformity correction based on radiograph will be summarized for the following:

- Angle deformity correction for hallux valgus deformity: Halux Valgus angle, Intermetatarsal angle, Distal Metatarsal Articular Angle
- Angle deformity correction for flatfoot or charcot: Mearys angle, Talonavicular Angle, Other
- Surgeon observed adverse event (Y/N)

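### The SAP plans no confidence interval for per-device failure, adverse-event and union proportions, and the protocol's Kaplan-Meier interval gives no usable limit for a device without events

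*SAP*

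**What the plan says.** SAP 3.1 treats the two kinds of variable differently. For quantitative variables, "The 95% confidence interval (CI) of the mean will be presented when the normality of the data is met". For the rest, "All qualitative variables, including those based on summaries (secondary elements), will be analyzed listing the proportions, frequencies, column and row totals" plus the share missing, and no interval. The table templates follow this split: Table 1.3 has a 95% CI column for age, weight, height and BMI. The surgeon evaluation template (Table 4.1) gives bony union and whether the product performed as intended as N and % only.

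For safety, SAP 6.6 says "Total frequencies and percentages of adverse events for each Wright device will be summarized for the following factors", and the list includes device-related events, device failure and SAEs. The adverse-event-by-device template has subjects with percentage, and events, with no interval.

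On survival, SAP 3.1 says "The proportion of device surviving at each visit will be summarized for each device" and SAP 6.6 adds "The rates for device failure will be the basis of the survival rates for each device". SAP Appendix 2A lists life tables for first device-related AE, device failure and death. No interval is named for any of these, and no template for the life tables is in the supplied text. Protocol 7.3 does promise one for survivorship: "The Kaplan Meier survival curve and the 95% Confidence Interval will be constructed". It names neither the variance formula nor a transformation.

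SAP 3.1 also reports that enrolment stopped with 122 patients in total, and it sets 10 implanted patients as the minimum for summarising a device.

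**The concern.** The study's stated aim is the safety and performance of each device separately, and the results go to regulatory authorities and notified bodies. At 10 or so patients, an observed 0% failure or 100% union is weak evidence, and the interval is what shows how weak. The SAP prints intervals for demographic means and none for the outcomes on which a safety conclusion would rest.

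The survival interval in the protocol does not fill the gap. It covers device-related AEs and reoperation for implant failure, and not union, product performance or SAEs. It also fails for a device with no events. The fewer patients a device has, the more a bare percentage hides.

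**Working it through.** **The plan's own precision figure.** Protocol 7.2 uses two-sided alpha 0.05, SD 0.313 and half-width 0.1: n = (1.96 × 0.313 / 0.1)² = 37.63, rounded up to 38. It reproduces. It concerns mean EQ-5D only. The SAP's reason for the 10-patient cut-off refers to the same EQ-5D parameters, so neither figure bears on the precision of an event proportion.

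**Exact limits at the SAP's sample sizes.** Inputs: two-sided alpha 0.05 (protocol 7.2), minimum n = 10 (SAP 3.1) and planned n = 40 (protocol 7.2); n = 15 and n = 20 are illustrative.

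- No events in n: the upper limit p solves (1 − p)^n = 0.025, so p = 1 − 0.025^(1/n).
  - n = 10: 1 − 0.6915 = 30.8%
  - n = 15: 21.8%
  - n = 20: 16.8%
  - n = 40: 8.8%
- Check: with a true rate of 0.3085, the chance of no event in 10 is (1 − 0.3085)^10 = 0.025.
- Union in 10 of 10: lower limit 0.025^(1/10) = 69.2%.
- One event in 10: 0.25% to 44.5%.
- Other upper limits for 0 of 10: one-sided 95% exact 25.9%, Wilson 27.8%, rule of three 3/10 = 30%. The message does not depend on the choice.

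**Kaplan-Meier with no events.** Greenwood's variance is S(t)² times the sum over event times of d / [n(n − d)]. With every d = 0, S(t) = 1 and the sum is 0.

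- Plain interval: 1 ± 1.96 × 0, that is 100% to 100%.
- Log form: log 1 = 0 with standard error 0, so it is equally degenerate.
- Log-log form: it needs log(−log 1) = log 0, which is undefined.

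None of these three forms gives a usable limit.

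**How often 0 of 10 would occur.** The documents state no failure, AE or non-union rate, so these true rates are assumptions. The chance is (1 − rate)^10:

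| Assumed true rate | Chance of 0 of 10 |
|---|---|
| 5% | 0.95^10 = 60% |
| 10% | 0.90^10 = 35% |
| 20% | 0.80^10 = 11% |

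**Denominators.** SAP Appendix 1 lists 43 devices against 122 patients. A patient can count for more than one device, so the number of devices that reach 10 cannot be worked out. SAP 3.1 computes rates on available data without imputation, so the evaluable number can fall below 10, and the limits then widen.

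**The case against.** The strongest reply is that SAP 3.1 declares the whole analysis descriptive, with no hypothesis tests, and that the tables print counts from which a reader can derive an interval. Reporting AEs as frequencies and rates also follows protocol 7.3, so it is no departure from the protocol. The primary endpoint, EQ-5D change, already has a planned interval. All of this is true. But an interval is estimation and not a test, and the SAP prints intervals for means under the same descriptive label. A reader could equally derive those from n and SD.

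Four stronger readings are tempting, and the documents do not support them:

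- **That failure and device-related AEs are reported only as crude percentages.** Life tables are listed for both. Without templates one cannot tell whether they would carry a standard error or interval; only the absence of a named one is established. The count-and-percentage description is complete for union, product performance and SAEs.
- **That the plan will print a zero-width survival interval.** That follows only for the plain or log form, and the protocol names no method. The SAP does not carry the Kaplan-Meier interval forward at all.
- **That 0 of 10 would be presented as proof of safety.** Protocol 5.2 does aim to show that the products are safe and effective, but no text says that a zero count will be read that way.
- **That zero events will be common.** This depends on event rates that the documents do not give, and it need not hold for frequent categories such as procedure-related events.

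One technical objection also stands: a crude binomial interval ignores unequal follow-up, and restricting it to patients followed to a set time discards the partial follow-up of censored patients. The fix has to say so.

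**Conclusion.** The point holds as an omission in the analysis method. No interval is planned for the per-device proportions that carry the safety and union conclusions, and the one event interval promised in the protocol gives no usable limit when a device has no events. At the SAP's minimum of 10 patients, 0 of 10 leaves true rates up to 30.8% open, and 10 of 10 leaves union rates down to 69.2% open. At the planned 40, the zero-event limit would have been 8.8%.

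These limits assume that all 10 patients are evaluable, with comparable follow-up, and use the two-sided 5% level of the protocol's sample-size calculation. How often a device will show no event is unknown. The primary EQ-5D analysis is unaffected. What changes is how much can be concluded about the safety and union results of devices with few patients.

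**What to change.** - In SAP 3.1 and 6.6, add exact (Clopper-Pearson) 95% intervals for the key per-device proportions: device failure, device-related AE, SAE, bony union and product performance as intended. Rows such as physical therapy or medication do not need one.
- Put them in the surgeon evaluation table and the adverse-event-by-device table. The latter is Table 5.1 in SAP 6.6 and in its template but Table 6.1 in the Appendix 2A list, where 5.1 is a life table. Reconcile the numbering.
- Carry the Kaplan-Meier 95% interval of protocol 7.3 into the SAP, and state a log-log interval for devices with events.
- For a device with no events, replace that interval with the exact upper limit for the event proportion among patients followed to the stated time. Show that denominator, and note that censored partial follow-up is not used.

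The cost is a few sentences in the SAP, one extra column in two tables and a specified interval in the survival output. No new data are needed. The downside is that safety and union results will look less certain.
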